2.4. Definition of Subgroups

There are 4 cohorts in this study. Subject information and safety data will be analyzed per cohort and vaccination schedule. The immunogenicity data will be presented per cohort (as shown in [Table 4](#)) and vaccination schedule. Only for Cohort 1, ELISA [units/mL] will also be presented by age stratum (aged ≤50 years and aged >50 years).

Table 4: Cohort, Age Group Combinations and Parameters

Cohort	Age Group	Analysis Parameters
1	≥18 years	
 - ELISA (units/mL) - VNA (IC₅₀ titers) - ELISpot - ICS - Ad26 VNA
	≤50 years	ELISA (units/mL)
	>50 years	
2a	18-50 years	
 - ELISA (units/mL) - VNA (IC₅₀ titers) - ELISpot - ICS - Ad26 VNA
2b	12-17 years	- ELISA (units/mL)

		
 - VNA (IC₅₀ titers) - ELISpot - ICS - Ad26 VNA
3	4-11 years	
 - ELISA (units/mL) - VNA (IC₅₀ titers) - ELISpot - ICS - Ad26 VNA

Ad26: adenovirus serotype 26 (vector); ELISA: enzyme-linked immunosorbent assay

ELISpot: enzyme-linked immunospot; IC₅₀: 50% inhibitory concentration; ICS: intracellular cytokine staining;
VNA: virus neutralization assay;

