### **Unknown Risks**

There are no clinical data on the use of either vaccine (Ad26.ZEBOV or MVA-BN-Filo) in:

- Pediatric subjects (<18 years);
- Pregnant or nursing women;
- Adults >50 years;
- Immunocompromised subjects (including those with HIV infection).

There may be other serious risks that are not known.

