The 3 different time intervals (of 28, 56 or 84 days) between the prime and the boost vaccination will be evaluated for safety and tolerability as well as for immunogenicity. These 3 prime-boost regimens will differ only in the timing of the boost vaccination, while the dose of each vaccine and the sequence of vaccination will be identical. The prime vaccine consists of Ad26.ZEBOV at a dose of  $5 \times 10^{10}$  vp and the boost vaccine consists of MVA-BN-Filo at a dose of  $1 \times 10^8$  infectious units (Inf U, nominal titer). The MVA-BN-Filo dose to be used corresponds to the dose of  $1 \times 10^8$  TCID50 that is used in the current Phase 1 studies. In the Cohort 1 substudy, the third vaccination consists of Ad26.ZEBOV at a dose of  $5 \times 10^{10}$  vp.

This Phase 2 study will be conducted to enlarge the safety and immunogenicity database for the Ad26.ZEBOV and MVA-BN-Filo prime-boost regimens and to extend the population studied in Phase 1 to include elderly subjects (>50 to 70 years inclusive), HIV-infected subjects, and healthy children (in 2 age strata) in order to cover a large spectrum of the population that would receive a vaccine in a future outbreak setting (ie, mass or ring vaccination). In this Phase 2 study, healthy adult subjects will also be included, ie, the population studied in the Phase 1 studies and in the Phase 2 study performed in Europe (VAC52150EBL2001). In addition, administration of a third vaccination with Ad26.ZEBOV in the Cohort 1 substudy will extend the findings to an African population and confirm the immunogenicity profile from a Phase 1 study (see Section 3.2).

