## **2. OBJECTIVES AND HYPOTHESIS**

### **2.1. Objectives**

#### **Primary Objective**

The primary objective is to assess the safety and tolerability of different vaccination schedules of Ad26.ZEBOV and MVA-BN-Filo administered IM as heterologous prime-boost regimens on Days 1 and 29, Days 1 and 57, or Days 1 and 85, in healthy adults, including elderly subjects, and on Days 1 and 29 and Days 1 and 57 in HIV-infected subjects and healthy children in 2 age strata.

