## 5. TREATMENT ALLOCATION AND BLINDING

### Vaccination Schedule Allocation

Based on the subject's demographics, a subject will be enrolled in one of the cohorts at study entry. Central randomization will be implemented in this study. In Cohort 1, subjects will be enrolled in parallel and randomized in a 1:1:1 ratio to Groups 1, 2 and 3 at baseline until a target of 132 subjects have been included in Group 3. Afterwards, randomization in this cohort will proceed in a 1:1 ratio to Groups 1 and 2. In Cohorts 2a, 2b, and 3, subjects will be enrolled in parallel and randomized in a 1:1 ratio to Groups 1 and 2 at baseline. Subjects will be randomly assigned to groups within cohorts (stratified by PBMC sampling capability of the selected sites), and within groups and age strata randomly assigned to Ad26.ZEBOV and MVA-BN-Filo, or placebo in a 5:1 ratio, based on a computer-generated randomization schedule prepared before the study by or under the supervision of the sponsor. The randomization within each group will be balanced by using randomly permuted blocks. Within Cohort 1, there will be stratification by age group (adults:  $\geq 18$  to  $\leq 50$  years of age, versus elderly:  $> 50$  years of age). The interactive web response system (IWRS) will assign a unique code, which will dictate the assignment and matching vaccination schedule for the subject. The requestor must use his or her own user identification and personal identification number when contacting the IWRS, and will then give the relevant subject details to uniquely identify the subject. For participants of the substudy, subjects who received Ad26.ZEBOV and MVA-BN-Filo will receive Ad26.ZEBOV as third vaccination. Subjects who received placebo will receive placebo as third vaccination.

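### Adults over 50 are in the primary safety objective and form a randomisation stratum, but the SAP plans no safety summary by age stratum

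*SAP*

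**What the plan says.** The primary objective in Protocol 2.1 covers safety and tolerability "in healthy adults, including elderly subjects, and on Days 1 and 29 and Days 1 and 57 in HIV-infected subjects" and in children. Protocol 1.3 gives as one reason for the study "to extend the population studied in Phase 1 to include elderly subjects (>50 to 70 years inclusive"). Protocol 1.2.4, under Unknown Risks, opens with "There are no clinical data on the use of either vaccine (Ad26.ZEBOV or MVA-BN-Filo) in", and the list that follows includes adults older than 50 years. On randomisation, Protocol 5 says "Within Cohort 1, there will be stratification by age group", with the cut at 50 years, and subjects are "within groups and age strata randomly assigned to Ad26.ZEBOV and MVA-BN-Filo, or placebo in a 5:1 ratio". SAP 1.5 repeats this.

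SAP 2.4 sets the level of the safety analysis: "Subject information and safety data will be analyzed per cohort and vaccination schedule". For Cohort 1, ELISA "will also be presented by age stratum" (up to 50, and over 50). Table 4 of the SAP gives the age split for no other parameter.

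Later sections do not restore an age split for safety. SAP 7 presents safety by cohort and then schedule. SAP 7.1.3 gives adverse event tables by schedule and period, and also pooled by vaccine dose. SAP 7.2.3 gives laboratory tables by regimen and period, again also pooled by dose. Protocol 11.5 plans no age split, and SAP 3 does not raise the point. The only other planned output by age group is the demographic count in SAP 5.3.

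**The concern.** The trial brings several new populations into the programme. HIV-infected subjects, adolescents and children each have a cohort, and so each has its own safety tables with a placebo group. Adults over 50 sit inside Cohort 1 and have none. The SAP reports the age stratum for a secondary immunogenicity endpoint but not for safety, which is the primary one.

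At stake is whether the report can describe reactogenicity, adverse events and laboratory abnormalities in people over 50 as such. A pooled Cohort 1 rate is weighted by the age mix. If most of the cohort is 50 or younger, a higher rate in the older stratum moves the pooled figure only a little. The comparison that would show it already exists by design, because the 5:1 allocation was made within age strata.

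**Working it through.** **Inputs from the documents.** Cohort 1 active: 220 + 220 + 110 = 550. Cohort 1 placebo: 44 + 44 + 22 = 110 (Protocol Table 1). Protocol 11.2 states one-sided 97.5% upper limits for an event that is not observed.

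**Reproducing the plan's figures.** With zero events in n subjects the upper limit is 1 − 0.025^(1/n).

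| n | Computed | Protocol 11.2 |
|---|---|---|
| 55 | 6.49% | 6.5% |
| 110 | 3.30% | 3.3% |
| 220 | 1.66% | 1.7% |
| 440 | 0.835% | 0.8% |
| 550 | 0.668% | 0.7% |
| 880 | 0.418% | 0.5% |

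The formula reproduces the plan's figures to rounding, except that the plan's 0.5% for n = 880 is a looser bound than the computed 0.418%. The plan gives no such figure for subjects over 50.

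**Assumption.** The readable text gives no target, minimum or cap for subjects over 50, so I take shares of 5%, 10% and 20% of Cohort 1. Placebo counts apply the same share to 110. The last column is the probability of seeing at least one event at a true incidence of 1%, 1 − 0.99^n.

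| Share over 50 | Active over 50 | Placebo over 50 | Zero-event upper limit | P(at least one) at 1% |
|---|---|---|---|---|
| 5% | 28 | about 6 | 12.3% | 25% |
| 10% | 55 | 11 | 6.5% | 42% |
| 20% | 110 | 22 | 3.3% | 67% |

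All 550 active subjects give a limit of 0.7%, but that limit describes the mixture of ages.

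**Dilution, with assumed event rates.** Suppose an event occurs in 30% of active subjects over 50 and 15% of younger ones. The pooled rate is 15% + share × 15%, that is 15.75%, 16.5% or 18.0% at the three shares. A doubled rate moves the pooled figure by 0.75, 1.5 or 3 percentage points.

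**What the added table would show in the same example.** Exact (Clopper-Pearson) 95% intervals for the active stratum over 50:
- 8/28 (28.6%): 13.2% to 48.7%, which still includes 15%.
- 16/55 (29.1%): 17.6% to 42.9%, which excludes 15%.
- 33/110 (30.0%): 21.6% to 39.5%, which excludes 15%.

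So the stratum table can reveal a doubling at a share of 10% or 20%, but might not at 5%.

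**The case against.** The SAP breaks no promise in the protocol. The objective treats healthy adults, including the elderly, as one population. Protocol 11.5 promises adverse event summaries by group and none by age. The study is descriptive with no formal testing, and stratifying the randomisation does not oblige anyone to produce stratified tables. All of that stands. The point is therefore a gap against the study's own objective and rationale, not a departure from the protocol.

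A reader might infer that the trial yields no safety information on older subjects. The documents do not support that. These subjects are in the full analysis set and every pooled Cohort 1 table. SAP 7.1 lists all reported adverse events. SAP 7.1.3 adds narratives for serious, fatal and immediate reportable events, those leading to discontinuation of vaccination, and related Grade 3 events. Abnormal laboratory findings are listed under SAP 7.2.3. But listings and narratives do not give a planned rate, an interval or a comparison with placebo.

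A reader might also infer that the number of older vaccinees stays hidden. It does not: SAP 5.3 tabulates age group for Cohort 1, and SAP 5 puts that table on the full analysis set by schedule, the same set used for safety.

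Nor does the Unknown Risks statement mean no relevant experience at all. It concerns Ad26.ZEBOV and MVA-BN-Filo. Protocol 1.1.2.2 reports MVA-BN-based vaccines in populations that included the elderly.

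Finally, small numbers may limit what an age table can show. That affects its precision. It is not a reason to omit it, since a descriptive table needs no power and an exact interval makes the imprecision plain.

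**Conclusion.** The point holds as an omission from the SAP: no planned safety summary is specific to subjects over 50, although the primary objective includes them, the protocol names them as a group without data on these two vaccines, and the randomisation was stratified to include them in balance. A difference from younger adults could be diluted in the Cohort 1 tables.

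The absence of the tables can be read directly from the SAP. The size of the consequence cannot, because the share over 50 is not in the readable text (the study schematic, which gives numbers per group, is not shown). The 5%, 10% and 20% shares and the 30% and 15% event rates are assumptions for illustration. On those shares, zero events would leave an upper limit of 12.3%, 6.5% or 3.3% for the stratum. This is a worthwhile improvement and does not call the pooled Cohort 1 safety analysis into question.

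**What to change.** In SAP 2.4 and Section 7, add for Cohort 1 summaries by age stratum (50 or younger, over 50) of solicited adverse events, unsolicited adverse events, Grade 3 events, serious and immediate reportable events, and laboratory abnormalities. Show active and placebo side by side, pooled over schedules within stratum, with the number vaccinated and exact 95% confidence intervals. State that any safety conclusion about subjects over 50 rests on those figures and not on the pooled cohort.

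Pooling over schedules matters. At a 10% share, a single schedule would have only 22 active subjects over 50 in Group 1 or 2 and 11 in Group 3.

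The cost is SAP wording and a rerun of existing tables by a variable already used for randomisation, demographics and ELISA. No new data are needed. The drawback is precision: intervals will be wide, the elderly placebo group may be very small (about 6, 11 or 22 at the assumed shares), and at a low share the tables may not separate even a doubled rate. They should be labelled descriptive.

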3. CHANGES TO THE PLANNED ANALYSIS

- Even in the absence of baseline immunogenicity samples, the post-baseline samples are of interest. Therefore, the immunogenicity analysis set is redefined to include subjects without baseline immunogenicity samples, provided that at least 1 post-vaccination evaluable immunogenicity sample is available for the subjects.
- Because different levels of post boost immunogenicity response are expected for different vaccination schedules, the per protocol analysis set is redefined to exclude subjects whose boost vaccination falls outside the protocol-defined window. Similar to the immunogenicity analysis set, the per protocol analysis set is also refined to include subjects without baseline immunogenicity samples.

4. INTERIM ANALYSIS AND DATA MONITORING COMMITTEE REVIEW

An independent data monitoring committee (IDMC) was instituted prior to the start of the study. The IDMC periodically reviewed safety data to ensure progressive safety of the subjects. The progression to a next cohort in the study was based on the favorable IDMC review of safety data. See the IDMC charter³ and the associated SAP⁴ for further details. For all cases, the data package and analysis results that contained any piece of unblinding information were kept in a strictly confidential place, with access for IDMC and the independent statistical support group members only until unblinding of the study by the sponsor.

The current SAP is applicable to the interim and final analyses. In each cohort, after completion of the 6-month post-boost visit by all subjects, an interim analysis will be conducted on safety and selected immunogenicity data and the cohort will be unblinded to the sponsor. Nevertheless, study-site personnel, subjects and sponsor personnel involved in subject level data review will remain blinded until the last subject in that cohort has completed the study. For the Cohort 1 substudy (ie, subjects who received the third vaccination), an additional interim analysis may be performed when all those subjects have completed the 6-month post-third vaccination visit, or discontinued earlier. Note that planned interim analyses may be combined with a subsequent analysis, if deemed necessary (eg, when the dates of 2 planned analyses are very close). On the other hand, additional interim analyses may also be performed during the study for regulatory purposes or for informing future vaccine-related decisions in a timely manner. The final analysis will be performed when all subjects have completed the last study-related visit or discontinued earlier (including subjects participating in the Cohort 1 substudy).

5. SUBJECT INFORMATION

Subject information will be analyzed based on the full analysis set. In general, the data will be presented by cohort and vaccination schedule

5.1. Disposition Information

The number and percentage of subjects randomized, vaccinated and entered in each analysis period will be tabulated. Subject assignment to vaccination schedule will be provided in a data listing (including the assigned vaccination schedule and the actual vaccination schedule).

Furthermore, the number and percentage of subjects in the full analysis set who completed and those who discontinued together with the reason(s) for discontinuation will be tabulated and listed. This will be done for completion/discontinuation from study vaccination and from the trial.

5.2. Protocol Deviations

Subjects with protocol deviations will be identified prior to the database lock. The major protocol deviations will be summarized by deviation category. A listing of the major protocol deviations will also be generated. The deviations that have the potential to influence immune response will be flagged in the listing.

5.3. Demographics and Baseline Characteristics

The following demographic characteristics will be summarized.

- Sex (Female/Male)
- Age (years)
- Age group (≤ 50 years versus > 50 years), only for healthy adult and elderly subjects (Cohort 1)
- Race
- Ethnicity
- Height (cm)
- Weight (kg)
- Body mass index (BMI, kg/m^2), calculated from baseline height and weight, only for subjects aged > 11 years
- Weight-for-age percentile at baseline, only for children aged 4 to 11 years using Centers for Disease Control and Prevention (CDC) Clinical Growth Chart⁵

To obtain the weight-for-age percentile for children aged 4 to 11 years, the z-score (z) will first be determined as:

$$z = \frac{\left(\left(\frac{\text{weight}}{M} \right)^L - 1 \right)}{(S \times L)}.$$

Where L, M and S denote the power in the Box-Cox transformation, median and generalized coefficient of variation, respectively. The L, M and S are the values from the appropriate CDC table⁶ corresponding to the age in months of the child. Note that age is listed in the table at the half month point for the entire month. For instance, 30.5 months represents 30.0-30.99 months (or 30.0 month up to but not including 31.0 months of age). The percentile corresponding to the calculated z-score will then be obtained based on the Standard Normal distribution.

For example, to obtain the weight-for-age z-score of a 4-year-old male who weighs 16.5 kg, the L, M and S values from the appropriate (WTAGE: CDC Clinical Growth Chart Percentile Data File⁶) table are $L=-0.915241589$, $M=16.31676727$, and $S=0.11995532$. Using the above formula, the calculated z-score for this child is 0.093. This z-score corresponds to the 54th percentile.

5.4. Prior and Concomitant Medications

The analysis of pre-study and concomitant therapies will be based on the World Health Organization (WHO) drug coded terms as provided in the clinical database. If the coded term for a concomitant medication is missing, then the reported term will be used and flagged in the table. The concomitant therapies will be tabulated per period. Additionally, a listing of all pre-study and concomitant therapies will be provided. There will be special attention to analgesics/antipyretics (such as acetaminophen, non-steroidal anti-inflammatory drugs [NSAIDs] and aspirin) administered during the first 8 days (including the day of the vaccination) following each vaccination. Special attention will also be given to HIV-related concomitant therapies (only for HIV-infected subjects, Cohort 2a).

Based on their start and stop dates, concomitant therapies will be reported in each analysis period during which they were applied. For missing or partial start/stop dates the following allocation rules will be applied:

- In case of partial start or stop dates, the concomitant therapy records will be allocated to analysis periods using the available partial information, without imputations. If, for example, only month and year are available, these will be compared to the month and the year of the analysis periods, and the concomitant therapy record will be allocated to the period(s) where these date parts match.
- In case of a completely missing start date, the concomitant therapy will be considered as having started before the trial.
- In case of a completely missing end date, the concomitant therapy will be considered as ongoing at the end of the trial.

Remark: In addition to the date information, time information is considered to allocate concomitant therapies to periods and/or phases, if available.

6. IMMUNOGENICITY

6.1. Endpoints

Secondary Endpoint:

Binding antibody levels elicited by vaccination using EBOV GP ELISA at 21 days post boost.

Exploratory Outcomes:

Several exploratory objectives were specified in the CTP¹. Those objectives will be investigated depending on the availability of the response outcome. The exploratory response outcomes could include but may not be limited to the following:

- Humoral immune responses against EBOV GP as measured by:
 - ELISA (units/mL), collected at all timepoints (as specified in the CTP¹).
 - Neutralizing antibody response in titers that inhibit viral infection by a certain percentage (IC₅₀), collected at all timepoints (as specified in the CTP¹).
- Cellular immune responses against EBOV GP as measured by:
 - Number of interferon (IFN)-γ producing T cells (using ELISpot), collected at baseline, pre-boost, 21 days post boost, 180 days post boost and Day 365 post prime.
 - Percentage of CD4+ T cells producing IFN-γ, tumor necrosis factor-α (TNF-α) and/or interleukin (IL)-2 (using ICS), collected at baseline, pre-boost, 21 days post boost, 180 days post boost and Day 365 post prime.
 - Percentage of CD8+ T cells producing IFN-γ, TNF-α and/or IL-2 (using ICS), collected at baseline, pre-boost, 21 days post boost, 180 days post boost and Day 365 post prime.
- Anti-vector neutralizing antibody responses as measured by Ad26 VNA (serum titers of neutralizing antibodies to Ad26 vector 90% inhibitory concentration [IC₉₀]), collected at baseline.

6.2. Immunogenicity Against the Insert

6.2.1. Humoral Immune Responses

6.2.1.1. Parameters

Humoral immune responses, as measured by the following assays, will be analyzed:

- **Binding antibody responses using Filovirus Animal Nonclinical Group (FANG) ELISA:** Quantification of antibodies binding to EBOV GP using the ELISA units/mL readout.

In addition, the following will be defined for ELISA (units/mL) binding antibody responses:

- **Sample interpretation:** A sample will be considered positive, if the value is above the lower limit of quantification (LLOQ).
- **Responder:**
 - If sample interpretation is negative at baseline but positive post-baseline and the post-baseline value is greater than 2.5×LLOQ; OR
 - If sample interpretation is positive at both baseline and post-baseline and there is a greater than 2.5-fold increase from baseline (2.5-fold increase on the original scale).
- **Neutralizing antibody responses using VNA:** titers of EBOV GP-specific neutralizing antibodies (unit: 50% inhibitory concentration [IC₅₀]).

For VNA (IC₅₀) responses, the following will also be defined:

- **Sample interpretation:** a sample is considered positive if the value is greater than both the assay-specific LLOQ and $3 \times$ (amphotropic murine leukemia virus [aMLV]). Otherwise, the sample is considered negative.
- **Responder:**
 - If sample interpretation is negative at baseline but positive post-baseline and the post-baseline value is greater than $2 \times$ LLOQ; OR
 - If sample interpretation is positive at both baseline and post-baseline and there is a greater than 2-fold increase from baseline (2-fold increase on the original scale).

Important: The pseudovirions used in the pseudo VNA (psVNA) are constructed using an HIV-genomic luciferase vector. During assay validation, a high non-EBOV GP-specific background signal was observed for 1 out of 3 HIV-positive sera tested. Hence, the accuracy of the quantitative measurement of the neutralizing antibody response can be affected in HIV+ serum samples. Therefore, the above responder definition will not be used for the HIV-infected cohort and only a qualitative readout of the psVNA will be reported for the HIV-infected cohort, using the VNA sample interpretation to classify a sample as either negative or positive.

